- d) Patients giving informed consent.

2) Exclusion Criteria:

Patients who have or are:

- a) An inability to cooperate during the block placement.
- b) Any neuropathy
- c) Diabetes
- d) Documented kidney disease
- e) Documented Hepatic disease

- f)** A lack of or inability to give informed consent.
- g)** Currently incarcerated.
- h)** Pregnancy

3) Consent:

- a) The study will be explained to the patient's satisfaction, their questions will be answered, and informed consent will be obtained from the patient after explanation of the risks, benefits, and alternatives.
- b) Once the patient has consented to the study, they will be included in the study and followed throughout.
- c) Patients with failed blocks will be included in the intention to treat analysis.
- d) If the block is unable to be placed due to infection at the site, poor visualization of structures with the ultrasound, inability to obtain study drugs within a reasonable time frame, or unexpected operator difficulty in placing the block, the patient will not be included in the intention to treat analysis and dropped from the study.

4) Randomization:

- a) A computerized random number generator will be used by a staff of the Anesthesia Department not involved with the study. They will create a randomized numbered sequence with four groups (A, B, C or D) that will be given to the pharmacy team. This will be used to fill study syringes in the sequence according to the randomization schema.
- b) The UIHC Pharmacy will compound the study drugs and will fill and label the coded study syringes.
- c) Coded study syringes must be created and delivered within 30 minutes of the physician's request.
- d) The Pharmacy will keep a record of which patient received each coded syringe and the solution they contained.
- e) They will be given to the practitioner at the time of block placement.
- f) Practitioners will perform the block using the pharmacy coded study drug.

5) Masking:

- a) Masking will be accomplished by using coded labels on the study mixtures.
- b) At the end of the study enrollment, information given to the statistical analyst will be blindly coded as groups A, B, C or D for data analysis.
- c) The Pharmacy will keep the group codes until after data analysis is complete.
- d) The anesthesiologist and nurse assistants will be masked to the study mixtures.
- e) Any assisting anesthesia Staff, Fellows, Residents, CRNAs, SRNAs, or medical students will be masked to the study mixtures.

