- d)** Using sterile technique, cleaning the skin with tinted chlorhexidine and with the operators wearing caps, masks, and sterile gloves. The ultrasound probe will have a sterile sheath over it. Sterile ultrasound gel will be used.
- e)** With ultrasound guidance and nerve stimulator from 0.2 mA to 2.0 mA using a sterile Arrow 90mm insulated stimulation needle (StimuQuick).
- f)** If we are unable to stimulate the brachial plexus at the trunk level with the nerve stimulator, we will place local anesthetic in the region where the brachial plexus nerves are visualized using ultrasound based on the practitioner's experience with ultrasound-guided interscalene (brachial plexus trunks) nerve blocks.
- g)** Block start and end times will be recorded. Start time begins at block needle insertion. Stop time is the time of nerve block-needle withdrawal.
- h)** All patients will be monitored with blood pressure, pulse oximetry, ECG and have 2 liters per minute of oxygen administered by nasal cannula.
- i)** Emergency resuscitation equipment, intralipid, and emergency medications are present and immediately available for patient safety.

- j) Anesthesiologists will be present and/or immediately available should resuscitation efforts be necessary in the unlikely event of drug toxicity, cardiac arrest, or other adverse event.
- k) Any adverse outcomes (listed in “stopping rules” #23 below) will be reported to the Safety Monitors on the day it happens.
- l) The use of rescue blocks in the PACU will be counted and analyzed.

8) Statistics

- a) For our **primary outcome**, we will use ANOVA or Kruskall-Wallis test, after checking the normality of the data, to compare the duration of the analgesic block. If we find a difference among all 4 groups, we will use 2-sample t-test or Mann-Whitney U-test to explore differences between the individual groups.
- b) For our continuously distributed **secondary outcomes**, given that outcomes will be observed on every patient, we will use ANOVA or Kruskall-Wallis test. For outcomes with categories (nausea and vomiting and blood pressure), we will use the chi-square test. Similarly, we will explore the different group or groups using chi-square test or Fisher’s Exact test.
- c) We based our estimates upon Cumming’s, Candido’s and Casati’s previous studies and our clinical experience. We have estimated the expected additional analgesic time between the three groups.

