- d) Using the above parameters, a sample size is 40 per group with 4 total groups calculates to a sum of 160 subjects while using 90% power and 0.05 type I error rate.

9) Safety Monitoring:

- a) An Anesthesiology Faculty member who is not involved in the study will act as safety monitor and will review the data and any complications when half of the patients (n = 80) have been completed.

10) Stopping Rules:

- a) Any incidence of patient complications that occur with an incidence higher than published data for the following complications for peripheral nerve blocks will be enough cause for the Safety Monitors to stop the study(31, 32). Numbers in parentheses below are the highest incidence reported in the referenced article for peripheral nerve block complications. The highest incidence of complications was reported to be from the supraclavicular block, which we will not be performing. We are relying on results reported from our own regional anesthesia follow-up clinic. This is a clinic developed here to see patients with troublesome complications of peripheral nerve blocks. The complication rates have been reviewed and studied since the clinic inception over 4 years ago(33). We are erring on the side of caution by using higher complication rates of the supraclavicular adverse event reports.
- b) Published Peripheral Nerve Block Complication rates:
 - i) Seizure (26.3/10,000)
 - ii) Cardiac arrest (Code Blue) (15.9/10,000)

- iii)** Respiratory Failure (15.9/10,000)
- iv)** Peripheral neuropathy (32/10,000)
- v)** Patient death (15.9/10,000)

References:

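### Patients whose block is attempted but not placed are dropped with no safety exception, so a delayed complication could go undetected and its place in the stopping-rule count is undefined

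*Combined protocol and SAP*

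**What the plan says.** The Consent section makes three statements about who stays in the trial.

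- Item b): "Once the patient has consented to the study, they will be included in the study and followed throughout".
- Item c): "Patients with failed blocks will be included in the intention to treat analysis".
- Item d) lists the exceptions, starting "If the block is unable to be placed due to infection at the site, poor visualization of structures with the ultrasound". It goes on to late availability of study drug and to "unexpected operator difficulty in placing the block". In all four cases "the patient will not be included in the intention to treat analysis and dropped from the study".

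Four other places bear on safety.

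- Techniques k): an adverse outcome on the stopping list "will be reported to the Safety Monitors on the day it happens".
- Safety Monitoring a): an independent faculty member "will review the data and any complications when half of the patients (n = 80) have been completed".
- Stopping Rules a): the trigger is "Any incidence of patient complications that occur with an incidence higher than published data". Item b) lists rates from 15.9 to 32 per 10,000, with peripheral neuropathy the highest. No population is defined for numerator or denominator.
- Definitions, under the analgesic, sensory and motor block durations: a telephone call within three days, described as collecting the patient's recorded times. No other post-discharge contact is scheduled.

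**The concern.** The wording of item d) goes beyond an analysis set: the patient leaves the study, and nothing is kept back for safety. That would matter little if all four reasons arose before any exposure. Operator difficulty, however, describes trouble while the block is being placed. Techniques g) starts the block at needle insertion, and Randomization e) hands over the coded syringes at block placement. Needle passes, and possibly some injection, can therefore come before removal.

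At stake is a complication that is noticed only after discharge. If nobody contacts the patient, same-day reporting has nothing to report. Such a patient is also naturally read as not being one of the 80 completed patients who trigger the only scheduled review. If the event did come to light, the plan gives no rule for whether it enters the incidence that is compared with the thresholds.

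**Working it through.** **Step 1. Who can be exposed and then dropped.** The four reasons in item d), set against the rest of the plan:

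| Reason | Exposure before removal? |
|---|---|
| Infection at the site | Ordinarily seen before needle entry |
| Study drug not available in time | Ordinarily known before needle entry |
| Poor ultrasound view | Often seen at scanning; may emerge later |
| Unexpected operator difficulty | Can arise after needle entry |

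Failure to stimulate the plexus is not in itself a reason to abandon, since Techniques f) then places the drug under ultrasound. The group of interest is mainly the last row.

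**Step 2. What one event does to the rule.** The plan gives no worked figure here to reproduce. The inputs are the thresholds in Stopping Rules b), the 80 patients in Safety Monitoring a) and the 160 in Statistics d).

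Observed incidence with one event = 1/n:

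- n = 80: 1/80 = 125 per 10,000
- n = 160: 1/160 = 62.5 per 10,000

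Both exceed every threshold (15.9, 26.3 and 32 per 10,000). The smallest n at which one event would not exceed its threshold is 1/threshold, rounded up:

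- Neuropathy: 10,000/32 = 312.5, so 313
- Seizure: 10,000/26.3 = 380.2, so 381
- Cardiac arrest, respiratory failure, death: 10,000/15.9 = 628.9, so 629

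All are above 160. Adding the dropped patients to the denominator changes nothing: with 8 of them (assumed), 1/(160 + 8) = 59.5 per 10,000, still above 32. So if the only neuropathy in the trial occurs in a dropped patient, counting it meets the criterion and leaving it out gives an incidence of zero.

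**Step 3. How likely that is.** The documents give no number of abandoned blocks, so m is an assumption. For m patients at rate p, P(at least one) = 1 − (1 − p)^m.

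| m (assumed) | Share of 160 | p = 0.0032 (protocol) | p = 0.01 (assumed) |
|---|---|---|---|
| 4 | 2.5% | 1.3% | 3.9% |
| 8 | 5% | 2.5% | 7.7% |
| 16 | 10% | 5.0% | 14.9% |

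For example, 1 − 0.9968^8 = 0.0253. The protocol's 32 per 10,000 is a rate for peripheral nerve blocks in general. The documents do not say whether abandoned attempts carry more or less risk, so the last column only shows the sensitivity.

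**The case against.** A reader might infer that dropped patients are excluded from the stopping-rule count and from what the monitor sees. The documents do not say so. Techniques k) and Stopping Rules a) are not limited to the intention-to-treat set, and Safety Monitoring a) names complications separately from the data. A seizure, arrest or respiratory failure around the attempt would occur under the monitoring in Techniques h) to j) and would be reportable the same day. This stands, and it confines the concern to delayed events and to the silence about who is counted.

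A reader might also say that these patients lose their complication follow-up. That is too strong, because the three-day call is described as collecting block times and no complication question is specified for anyone. What they lose is the only scheduled contact at which a problem might come up. The institution's follow-up clinic, described under Stopping Rules, may see some of them, but nothing in the plan routes dropped patients there.

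Item d) can be read as an exception to item b) rather than a flat contradiction, and a partial injection that works poorly might be classed as a failed block and kept under item c). Both readings are fair, but neither is written down. The plan draws no line between a failed block and one that could not be placed once some drug has gone in.

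Finally, the fact that one event exceeds every threshold is a property of the stopping rule at this sample size, not of item d). An exceedance also gives the monitors grounds to stop; it does not compel them. Both points are correct. They mean that the outcome is sensitive to one patient, not that a wrong decision is likely.

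**Conclusion.** The point holds in limited form. Item d) removes, without a safety exception, consented patients of whom some may have been exposed to the needle or the study mixture, although item b) promises follow-up throughout. A delayed event such as peripheral neuropathy could go undetected in them, and the plan does not say whether they belong in the Stopping Rules incidence.

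The affected group is probably small. At an assumed 4 to 8 patients and the protocol's own neuropathy rate, the chance of at least one case is about 1.3% to 2.5%. The consequence is nevertheless decisive for the rule, because one case exceeds every threshold at n = 80 or n = 160. That rests on there being no other neuropathy in the trial. It does not follow that the trial will understate its risk, only that it could. The change is worth making because it is cheap and settles in advance how such a case would be handled.

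**What to change.** Reconcile Consent items b) and d). For any patient in whom the block needle was inserted or any study mixture injected, limit item d) to exclusion from the efficacy analysis, and state that:

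- the patient stays in a safety set made up of all attempted blocks;
- the patient receives the three-day call, with a question on complications;
- the patient counts in both numerator and denominator of the Stopping Rules incidence.

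The complication question should go to all patients, so that events are sought in the same way in everyone who enters the incidence. A call within three days will find only what has been noticed by then, so this narrows the gap without closing it.

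The cost is about one sentence of protocol text, a few extra calls, and one added question per call. The efficacy analysis is unchanged.

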- f) Patients will be masked to the study mixtures.
- g) Any person collecting and/or scribing the data will be masked to the study mixtures.
- h) Any person analyzing the data will be masked to the study mixtures.
- i) Once all the data has been collected and analyzed according to group code, the blinding on the study mixtures can be broken and the codes for the study mixtures made known.
- j) Safety monitors will not be masked to the mixtures. They can communicate with the pharmacy to unmask the mixtures for only themselves. They will not report the mixtures or pharmacy codes to anyone except for patient safety purposes.

k) The coded sample syringes will be kept for reanalysis in case there is any question of what mixture was given to any patient. The syringe contents can be tested by the pharmacy and a group code for that patient or set of patients will then be given to the analyst. The masking will remain intact.

6) Study Mixtures

a) The local anesthetic study mixtures volumes will be the same (32mL) and contained in two thirty-milliliter syringes with 16 mL in each. They consist of:

- i)** 0.75% Ropivacaine x 30mL (225 mg max dose) + 2 mL saline for a total volume of 32 mL
- ii)** 0.75% Ropivacaine x 30mL (225 mg max dose) with 300 mcg buprenorphine (1 mL) + 1 mL sterile saline for a total volume of 32 mL
- iii)** 0.75% Ropivacaine x 30mL (225 mg max dose) with 100 mcg/kg clonidine (0.1 mL) + 1.9 mL sterile saline for a total volume of 32 mL
- iv)** 0.75% Ropivacaine x 30mL (225 mg max dose) with 8mg dexamethasone (2 mL) + 0 mL sterile saline for a total volume of 32 mL.
- v)** *Note: If drug shortages occur during the study and we are unable to use the same concentration of any additive drugs (e.g. dexamethasone 10mg/mL instead of 4mg/mL), then a substitution will be allowed and the total volume in the syringe will be changed so that all syringes will be the same volume and final ropivacaine drug mass.*

7) Techniques:

All the blocks will be performed:

- a)** Either by, or under the direct supervision and direction of the Primary Investigator or regional anesthesia faculty listed on the investigation team.
- b)** In the Ambulatory Surgery Center at the University of Iowa Hospitals and Clinics using the posterior approach to the brachial plexus at the trunk level.
- c)** A timeout will be performed before the block to verify the patient, site of surgery and that we are blocking the correct side (already marked).

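### Consent, item d removes patients from the intention-to-treat analysis, probably after a sequence slot has been assigned, and the moment of randomization is not defined

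*Combined protocol and SAP*

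**What the plan says.** Three neighbouring items under Consent set the analysis population.

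- Item b: "Once the patient has consented to the study, they will be included in the study and followed throughout".
- Item c: "Patients with failed blocks will be included in the intention to treat analysis".
- Item d: if the block cannot be placed, "the patient will not be included in the intention to treat analysis and dropped from the study". Four reasons are listed: infection at the site, poor ultrasound view, and then "inability to obtain study drugs within a reasonable time frame, or unexpected operator difficulty in placing the block".

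Under Randomization, the sequence goes to pharmacy, which fills syringes in that order (item a). Syringes must be made and delivered within 30 minutes of the physician's request (item c), and they reach the practitioner when the block is placed (item e). Under Masking, operators, patients, data collectors and analysts are masked. Pharmacy holds the codes.

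Study Mixtures, item v foresees a supply problem: "If drug shortages occur during the study and we are unable to use the same concentration of any additive drugs". Its remedy is to allow a substitute and equalise syringe volumes.

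The documents do not say at which moment a patient is randomized, whether a removed patient's slot is reused, or whether removals will be counted by group.

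**The concern.** An intention-to-treat set keeps every randomized patient in the assigned group, so that the groups compared are those that randomization made. If some patients leave after a slot is assigned, the label is wrong and comparability must be argued for each reason of removal.

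Two of the four reasons deserve attention. Drug supply is settled in the pharmacy, where the contents are known, so masking the operator does not guard against imbalance there. Operator difficulty has no stated criterion. In particular, the text does not say whether a patient with part of the study drug injected is kept or removed. With no planned count of removals by group, a reader of the results could not tell whether the groups analysed match the groups allocated.

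**Working it through.** **1. Timing and possible dependence on arm, reason by reason**

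| Reason in item d | When it is likely to appear | Who or what decides | Could it depend on arm? |
|---|---|---|---|
| Infection at site | Possibly before the syringe request | Patient factor | No |
| Poor ultrasound view | Before or after the request | Masked operator | Not expected |
| Drug not obtained in time | After the request, when the next slot probably already fixes the mixture | Pharmacy | Plausible |
| Operator difficulty | At placement, when the coded syringe is at hand | Masked operator | Not expected |

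Supply is marked plausible because the plain mixture needs only ropivacaine and saline, while each other mixture needs its own additive. The shortage note deals with a changed concentration. It does not deal with a complete lack of an additive.

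**2. The plan's own figure**

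Statistics, item d gives "a sample size is 40 per group with 4 total groups" and "a sum of 160 subjects while using 90% power and 0.05 type I error rate". This cannot be reproduced, because item c offers only "We have estimated the expected additional analgesic time between the three groups", with no effect size or standard deviation. Working backwards instead, and assuming a two-sided two-sample t-test at 0.05, 40 per group gives 90% power at a standardized difference of d = 0.734. For the four-group ANOVA the corresponding value is Cohen's f = 0.301.

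**3. Precision if removals are balanced**

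No removal rate is given, so 5%, 10% and 20% per group, without replacement, are assumptions. The number analysed is n = 40 × (1 − q). Pairwise power uses the noncentral t with 2n − 2 degrees of freedom and noncentrality 0.734 × √(n/2). The last column is 40/(1 − q), rounded up.

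| q | n per group | Pairwise power | ANOVA power | Allocated per group to keep 40 |
|---|---|---|---|---|
| 0% | 40 | 90% | 90% | 40 |
| 5% | 38 | 88.4% | 88.3% | 43 |
| 10% | 36 | 86.7% | 86.3% | 45 |
| 20% | 32 | 82.4% | 81.4% | 50 |

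**4. Bias if removals fall on one group only**

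Suppose one group loses a fraction q, and the patients lost differ from that group's mean by k standard deviations. The mean of those who remain shifts by q × k/(1 − q) standard deviations. For q = 10% and k = 1 this is 0.10/0.90 = 0.111. With b for the shift and SE = √(1/40 + 1/[40(1 − q)]), the two-sided error rate under no true difference is Φ(−1.96 − b/SE) + 1 − Φ(1.96 − b/SE).

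| q | k = 0 | k = 0.5 | k = 1 |
|---|---|---|---|
| 5% | shift 0; 5.0% | 0.026; 5.2% | 0.053; 5.6% |
| 10% | shift 0; 5.0% | 0.056; 5.7% | 0.111; 7.7% |
| 20% | shift 0; 5.0% | 0.125; 8.2% | 0.250; 18.4% |

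The values of q and k are assumed. The table shows the condition for harm: bias needs both a loss that depends on arm and a prognostic difference. With k = 0 there is none.

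**The case against.** The other side has several good points.

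- **Timing is inferred.** Infection or a poor view may be found before any request, and in a supply failure no syringe was delivered. This stands. It is why the claim is limited to supply and operator difficulty and worded as probable. The missing definition is itself part of the defect.
- **Operator difficulty is bounded and masked.** A reader might infer that any hard block likely to fail can be discarded. The text does not support that: all four reasons sit under the condition that the block could not be placed, and a placed block that fails is kept under item c. Techniques, item f also directs injection under ultrasound when stimulation fails. Since the operator is masked, such removals should balance across arms. What remains is the unclear status of a partial injection.
- **Supply is not arm-dependent by design.** A reader might infer that supply removals must fall on adjuvant arms and never on plain ropivacaine. The shortage note provides a substitution that keeps the arm supplied, and the 30-minute limit applies to every syringe, so a delay can hit the plain group too. Only the uncovered case, complete lack of an additive, leaves a plausible route. Nothing ties supply failure to prognosis.
- **Inflation of the 25% effect cannot be read off.** One might count each removed adjuvant patient as zero duration and derive an inflated ratio to plain. That needs every removal to fall in one adjuvant arm, and equal removals on both sides leave the ratio unchanged. Duration runs from needle withdrawal, so it is undefined where no block was placed. The planned tests are also for any difference, not for a 25% margin.
- **Item d may be a specific exception to item b.** That reading reconciles who is followed. It does not make the intention-to-treat label correct.

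**Conclusion.** The point holds in a limited form. The set called intention to treat leaves out consented patients who were probably already assigned a sequence slot. Items b and d need to be reconciled, and the moment of randomization is undefined.

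The expected cost of operator-difficulty removals is precision: about 88%, 87% or 82% power at assumed losses of 5%, 10% or 20% per group, if 90% is read as pairwise power and removed patients are not replaced. Supply removals are the one plausible arm-dependent route. Whether they would bias the result cannot be determined from the documents, because neither their number, their distribution over groups nor their relation to prognosis is known. The change is worth making because it closes that route cheaply and makes the analysed set transparent. The documents do not show that the comparison is biased.

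**What to change.** 1. Define randomization as release of the next sequence number. Release it only after the site check, the ultrasound look and pharmacy confirmation that whichever of the four mixtures comes next can be supplied. Patients who fail any of these are screen failures before randomization.
2. From that point, analyse everyone given any study drug in the assigned group, including difficult blocks and partial injections.
3. Call this set modified intention to treat, and reword Consent, items b and d to match.
4. Report allocated patients with no drug injected by coded group (A to D) and reason. This keeps the masking intact. They remain outside the primary set because they have no starting time for duration, which is why the modified label and the count are needed.

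A sensitivity analysis that gives those patients the lowest rank is optional.

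The cost is protocol wording, a later release of the number, and one table. The small downside is that a few short durations stay in the primary analysis.

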**A PROSPECTIVE TRIPLE-MASKED RANDOMIZED
CONTROLLED TRIAL MEASURING ANALGESIA
DURATION OF DEXAMETHASONE, BUPRENORPHINE, OR
CLONIDINE WITH ROPIVACAINE FOR INTERSCALENE
NERVE BLOCK**

STUDY PROTOCOL

- 1) Protocol Title:** A prospective triple-masked randomized controlled trial measuring duration of buprenorphine, dexamethasone, clonidine with ropivacaine for interscalene block
- 2) Protocol Version:** 2.0
- 3) Protocol Initiated:** June 18th, 2012
- 4) Protocol Revision Date:**
- 5) Protocol Completed Date:** *pending*
- 6) Principal Investigator:** [name]
- 7) Research Team:** [name]; [name], MS; [name], MPT; [name]; [name].; All research team members must be IRB certified.
- 8) Study Design:** This is a prospective randomized controlled triple-masked study looking at the duration of nerve block analgesia when using the listed adjuvants plus ropivacaine versus plain ropivacaine alone.
- 9) Questions:**
 - a)** When providing a interscalene nerve block (ISB) for painful shoulder surgery using the following four regimens:
 - i)** 0.75% plain ropivacaine. The reference comparator.
 - ii)** A mixture of 0.75% ropivacaine with 300 mcg buprenorphine
 - iii)** A mixture of 0.75% ropivacaine with 0.1 mcg/kg clonidine
 - iv)** A mixture of 0.75% ropivacaine with and 8mg dexamethasone
 - b)** Compared to 0.75% plain ropivacaine, will the adjuvant mixture:
 - i)** Increase block analgesic duration?
(Defined as elapsed times from block-needle withdrawal until patient-reported time that they were first aware of painful sensation in the operated region of the limb.)
- 10) Hypothesis:**

- a) **Null Hypothesis:** Compared to plain ropivacaine, the adjuvant mixture:
 - i) Will not increase the nerve block analgesic duration time by 25% or more.
- b) **Alternate Hypothesis:** Compared to plain ropivacaine, the adjuvant mixture:
 - i) Will increase the nerve block analgesic duration time by 25% or more.

11) Primary Outcome:

- a) Our primary outcome is the time from nerve block-needle withdrawal to return of:

- i) Painful perception in the operated upon area of the limb.

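### The clonidine dose is 0.1 mcg/kg in the study questions but 100 mcg/kg in the pharmacy mixture, a 1000-fold contradiction that leaves the arm's dose undefined and the mixture line unsafe to compound from.

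*Combined protocol and SAP*

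**What the plan says.** Item numbers restart within the protocol, so places are given by heading as well.

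- **Questions (9, a, iii)** lists the clonidine regimen as "A mixture of 0.75% ropivacaine with 0.1 mcg/kg clonidine".
- **Study Mixtures (6, a, iii)** has 30 mL of 0.75% ropivacaine "with 100 mcg/kg clonidine (0.1 mL) + 1.9 mL sterile saline for a total volume of 32 mL".
- **Study Mixtures (6, a, ii and iv)** specifies the other two adjuvants "with 300 mcg buprenorphine (1 mL) + 1 mL sterile saline for a total volume of 32 mL" and "with 8mg dexamethasone (2 mL) + 0 mL sterile saline for a total volume of 32 mL". Both doses match those under Questions.
- **Randomization (4, b)**: "The UIHC Pharmacy will compound the study drugs and will fill and label the coded study syringes".
- **Masking (5, d)**: "The anesthesiologist and nurse assistants will be masked to the study mixtures".
- **Study Mixtures (6, a, v)** has a note that begins "If drug shortages occur during the study and we are unable to use the same concentration of any additive drugs". It permits substitution with an adjusted volume, but gives neither a dose nor a concentration for clonidine.

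The background section discusses clonidine without stating a dose. No cap, weight rule or stock strength appears anywhere.

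**The concern.** The two clonidine entries are both current protocol text and differ by three orders of magnitude. The mixture line is the more detailed of the two and is the one that reads as a compounding recipe. It carries the larger figure.

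Two things are at stake.

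- **Safety.** The syringes are coded and all arms have the same volume, so the person giving the block has no means of noticing a wrong clonidine dose. Taken literally, the mixture line calls for 1000 times the dose named in the study questions.
- **Interpretation.** Clonidine is one of three adjuvants compared with plain ropivacaine, with 40 of the 160 planned patients. The hypothesis asks whether it prolongs analgesia by at least 25%. From the protocol alone, neither a positive nor a null answer could be tied to a dose or repeated elsewhere.

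**Working it through.** **Inputs.** The doses (0.1 and 100 mcg/kg) come from Questions and Study Mixtures. The volumes (30 mL ropivacaine, 0.1 mL clonidine, 1.9 mL saline, 32 mL total) come from Study Mixtures. Body weight and clonidine stock strength are not in the document; weights of 50 to 120 kg are assumed.

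**1. Volumes.** 30 + 0.1 + 1.9 = 32 mL, as stated. The other arms also reach 32 mL (30 + 2; 30 + 1 + 1; 30 + 2 + 0). The total is right, but only while clonidine stays at 0.1 mL for every patient.

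**2. Ratio of the two doses.** 100 / 0.1 = 1000. This does not depend on body weight.

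**3. Does either dose fit 0.1 mL?** Dose = mcg/kg × weight; stock needed = dose / 0.1 mL.

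| Assumed weight | Dose at 0.1 mcg/kg | Stock needed | Dose at 100 mcg/kg | Stock needed |
|---|---|---|---|---|
| 50 kg | 5 mcg | 50 mcg/mL | 5,000 mcg | 50 mg/mL |
| 70 kg | 7 mcg | 70 mcg/mL | 7,000 mcg | 70 mg/mL |
| 80 kg | 8 mcg | 80 mcg/mL | 8,000 mcg | 80 mg/mL |
| 100 kg | 10 mcg | 100 mcg/mL | 10,000 mcg | 100 mg/mL |
| 120 kg | 12 mcg | 120 mcg/mL | 12,000 mcg | 120 mg/mL |

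The stock needed changes with weight in both cases. A per-kg dose cannot be a constant volume of one stock, so the 0.1 mL does not tell us which dose was meant.

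**4. Could a simple slip reconcile the lines?** Two candidates:

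- *The per-kg unit is stray and the dose is a flat 100 mcg.* The stock would have to be 100 / 0.1 = 1,000 mcg/mL. Per kg this is 100 / 120 = 0.83 to 100 / 50 = 2.0 mcg/kg. Against the 5 to 12 mcg implied under Questions it is 100 / 12 = 8.3 to 100 / 5 = 20 times too large.
- *The 100 is a stock strength in mcg per mL.* Then 0.1 mL holds 100 × 0.1 = 10 mcg for everyone, which is 10 / 120 = 0.08 to 10 / 50 = 0.2 mcg/kg. It equals 0.1 mcg/kg only at 100 kg.

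The second comes close to the Questions figure and the first does not. They differ from each other tenfold, and each requires rewriting at least one line. The document supports neither over the other.

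**The case against.** The strongest reply is that this is a drafting error no pharmacist would carry out. At 80 kg the literal instruction needs an 80 mg/mL stock, and a different stock at every other weight, so it invites a query. The other two adjuvants are flat doses in fixed volumes, which makes a flat clonidine dose the natural reading. The document does not say that the pharmacy works from this line and not from a worksheet of its own. The pharmacy must also record what each syringe held, coded samples are kept for testing, safety monitors can unmask, and patients are monitored with resuscitation equipment to hand.

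Part of this stands. No wrong syringe is shown, the 1000-fold figure compares two literal texts and is not the only plausible size of the error, and the dose actually given could probably be recovered afterwards from the records and samples.

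The rest does not remove the problem. A flat dose still leaves the lines in conflict, and the choice between flat readings is itself tenfold. The records and samples help only after injection. The planned safety review comes at 80 patients. Same-day reporting (Techniques, k) covers the events under Stopping Rules: seizure, cardiac arrest, respiratory failure, neuropathy and death. Blood pressure change is a secondary outcome and is not on that list. None of these safeguards fixes the dose before a masked operator gives it.

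**Conclusion.** The concern holds. The two stated clonidine doses differ by a factor of exactly 1000, and the mixture line pairs a weight-based dose with a fixed volume, which cannot be right for more than one body weight. The drug, the ropivacaine mass and the total volume of the arm are specified; the clonidine dose is not, and nothing in the document settles it. The absolute figures (5 to 12 mcg against 5 to 12 mg) rest on assumed weights of 50 to 120 kg; the ratio rests on no assumption. The hazard lies in the written instruction, and there is no evidence here of an overdose. It must be fixed before compounding.

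**What to change.** The sponsor and the pharmacy should decide the intended dose and enter it identically under Questions and Study Mixtures, with:

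- one figure with its units, stated as flat or per kg;
- the stock concentration;
- the clonidine volume, and a saline volume equal to 2 mL minus the clonidine volume, so that every syringe set still totals 32 mL;
- for a per-kg dose, variable volumes and a requirement that the patient's weight goes to the pharmacy with each request.

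The shortage note should say that the clonidine dose stays constant if the stock changes. The pharmacy's own compounding instructions should be checked against the corrected text. If any clonidine syringe has already been made, the pharmacy, which holds the codes, should establish the dose from its records or the retained samples, and that dose should be reported with the results.

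A flat dose needs a correction of a line or two and a pharmacy check. A per-kg dose also needs the weight passed on and a calculation done within the 30 minutes allowed for syringe delivery. Neither adds patients, visits or procedures, and masking is unaffected.
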